6.2.5.4 Sample collection

On days 2, 3, 4, 8, and 10 blood will be obtained. Approximately 16cc of blood will be collected for metabolomics after an overnight fast prior to breakfast. Urine and feces samples will also be obtained. Up to 15 ml of urine samples will be collected prior to 09:00h after an overnight fast starting at midnight. The first stool sample will be aliquoted and frozen.

6.2.5.5 Recording of diet

Participants will continue on their randomized diets. Participants will be instructed to consume only the food provided and no other food. Participants must eat all of the brownie and servings of sorbet provided. Participants will have access to additional food outside of the meals provided, however, the entire serving of the previous meal must have been consumed. The amount of food consumed will be recorded on the case report forms.

6.2.5.6 Timing of meals

Breakfast will be served at 09:00h. Lunch will be served at approximately 12:30h and dinner at approximately 18:00h. A snack will be provided at 10:30h, 15:00h and 21:00h on Days 2-9. Participants will be expected to consume snacks by the next meal with the last snack consumed by midnight on Days 2-9. On Day 10, the 21:00h intervention snack will be provided in addition to the intervention and meal at 18:00h. Participants will be expected to finish each meal by the time of their next meal or snack. Lunch should be finished within 30 minutes. On Day 10, all food must be consumed by 19:30h. No food or beverage other than water is to be consumed between midnight and breakfast on Days 2-9 and between 19:30h and breakfast on Day 10.

6.2.5.7 Satiety Questionnaire

On days 2, 3, 5, 6, 9 and 10, participants will complete a standard food satiety questionnaire at 12:15h before lunch and at 13:00h following the completion of lunch.

6.2.5.8 Activity Level Maintenance

See Day 1 of inpatient procedures.

6.2.6 Day 11 of Inpatient Procedures (Visit 3.11)

All of the below procedures for day 11 will be the same for both study arms.

6.2.6.1 Vital Signs and Weight

See Day 2-3 of inpatient procedures.

6.2.6.2 Adverse Events

Participants will be queried for adverse events.

6.2.6.3 Concomitant medications

Consumption of concomitant medications will be recorded in the study records. Participants will not be permitted to take any medications that are listed in the exclusion criteria during the study.

6.2.6.4 Oral Glucose Tolerance Test

Participants will complete a 2.5 hour oral glucose tolerance test. This test will be completed prior to breakfast following a 12 hour fast.

6.2.6.5 Sample collection

Blood, urine, and feces samples will be obtained as described above. Up to 15 ml of urine samples will be collected prior to 09:00h after an overnight fast starting at midnight. Approximately 16cc of blood will be collected for metabolomics after an overnight fast prior to breakfast. The first stool sample will be aliquoted and frozen.

6.2.6.6 Flexible Sigmoidoscopy

Following the oral glucose tolerance test, each participant will undergo a sigmoidoscopy to obtain biopsies from the area of approximately 15 cm from the anal verge.

6.2.6.7 Recording of diet

Participants will be given their scheduled, randomized diets following the oral glucose tolerance test except during the flexible sigmoidoscopy. Participants will be instructed to consume only the food provided and no other food. Participants must eat all of the brownie and servings of sorbet provided. Participants will have access to additional food outside of the meals provided, however, the entire serving of the previous meal must have been consumed. The amount of food consumed will be recorded on the case report forms.

6.2.6.8 Timing of meals

The first meal will be served following the oral glucose tolerance test. All scheduled snacks and meals will be provided following the oral glucose tolerance test except during the flexible sigmoidoscopy. If the flexible sigmoidoscopy directly follows the oral glucose tolerance test, participants will be given their final meal before discharge.

6.2.6.9 Activity Level Maintenance

Participants will not be walked to maintain activity level.

6.2.6.10 PROMIS Scale

Participants will complete the PROMIS scale prior to eating their first meal.

6.2.6.11 Discharge

Participants will be discharged following the completion of the oral glucose tolerance test and the flexible sigmoidoscopy, and the collection of blood, urine, and stool or by 5pm. They will be given post-flexible sigmoidoscopy instructions. An AE log and a participant payment form will be completed. Participants will then be escorted out of the hospital.

6.3 Post-study follow-up

There will be three additional visits following the completion of inpatient visits.

6.3.1 Adverse Event Follow Up Phone Call (Visit 4)

The research team will contact the participant by phone once during the week following the completion of the inpatient procedures to assess for any new or unresolved adverse events.

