6.1.4 Sigmoidoscopy to obtain mucosal biopsy samples

On days 1 and 11, each participant will undergo a sigmoidoscopy to obtain biopsies from the area of approximately 15 cm from the anal verge, which correlates with approximately the rectosigmoid junction. No bowel preparation will be utilized prior to the sigmoidoscopy since it is unknown what affect the bowel preparation may have on the fecal microbiome or the mucosally adherent microbiome. No sedation medications will be administered.

16 biopsies obtained from the distal 20 cm of the colon will be collected; 4 placed in Carnoy solution for non-denaturing confocal microscopy, 4 flash frozen in liquid

nitrogen, 4 placed in RNAlater, and 4 will be kept fresh for immediate cell isolation studies. Additional biopsies may be taken (up to a total of 20), to replace lost/dropped/unusable biopsies (i.e., if the biopsy is too small), for quality control and/or for methods testing.

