6.2 Sequence of study activities

Visit Number	Visit 1	Visit 1.1	Visit 2	Visit 2.1	Visit 3											Visit 4	Visit 5	Visit 6
	-60 to -9	-7	-4	-3 to -1	1	2	3	4	5	6	7	8	9	10	11	24	48*	107*
Study Day																		
Food pick up			X															
Emulsifier free diet				X														
Randomized diet					X	X	X	X	X	X	X	X	X	X	X			
Satiety Questionnaire						X	X		X	X			X	X				
Record Calories Consumed					X	X	X	X	X	X	X	X	X	X	X			
DHQLI					X													
Fitbit Data Collection			X	X	X	X	X	X	X	X	X	X	X	X	X			
Walks (as needed)					X	X	X	X	X	X	X	X	X	X	X			
Weight	X		X		X	X	X	X	X	X	X	X	X	X	X			
Waist Circumference	X																	
CBC	X																	
CMP	X														X			
PT and INR	X																	
HbA1c	X																	
Fasting Lipid Panel	X																	
Vital Signs	X		X		X	X	X	X	X	X	X	X	X	X	X			
Physical Exam	X				X													
Medical History	X																	
24 hour recall x3		X																
Urine Collection	X		X		X	X	X	X	X	X	X	X	X	X	X			
Stool Collection			X		X	X	X	X	X	X	X	X	X	X	X		X	X
Stool Kit Pick Up	X		X											X		X		
Stool Kit Return			X		X											X	X	
Blood Collection			X		X	X	X					X		X	X	X		
PROMIS scale					X										X			
Oral glucose tolerance test					X										X			
Rectal swabs					X													
Sigmoidoscopy with biopsy					X									X				
Monitoring adverse events					X	X	X	X	X	X	X	X	X	X	X	X		
Concomitant medications	X		X		X	X	X	X	X	X	X	X	X	X	X			
AE Follow Up Phone Call																X		
Follow Up Questionnaire																	X	X

*Fitbit will be distributed at Visit 2 (4 days prior to admission to inpatient CHPS).

*Urine pregnancy test will be conducted for females at screening and Day 1 of inpatient procedures.

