6.3.2 One Month Follow-Up Sample Collection (Visit 5)

Participants will provide a stool sample 1 month (+/- 1 week) after discharge. Participants will return for a blood collection 1 month after discharge. Participants will complete a post study follow up questionnaire at this visit.

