An **adverse event** (AE) is any symptom, sign, illness or experience that develops or worsens in severity during the course of the study. Intercurrent illnesses or injuries should be regarded as adverse events. Abnormal results of diagnostic procedures are considered to be adverse events if the abnormality:

- results in study withdrawal
- is associated with a serious adverse event
- is associated with clinical signs or symptoms
- leads to additional treatment or to further diagnostic tests
- is considered by the investigator to be of clinical significance

Serious Adverse Event (SAE)

Adverse events are classified as serious or non-serious. A **serious adverse event** is any AE that is:

- fatal
- life-threatening
- requires or prolongs hospital stay
- results in persistent or significant disability or incapacity
- a congenital anomaly or birth defect
- an important medical event

Important medical events are those that may not be immediately life threatening, but are clearly of major clinical significance. They may jeopardize the participant, and may require intervention to prevent one of the other serious outcomes noted above. For example, drug overdose or abuse, a seizure that did not result in in-patient hospitalization or intensive treatment of bronchospasm in an emergency department would typically be considered serious.

All adverse events that do not meet any of the criteria for serious will be regarded as **non-serious adverse events**.

Adverse Event Reporting Period

The study period during which AEs must be reported is normally defined as the period from the initiation of any study procedures to the end of the study treatment follow-up. For this study, the study treatment follow-up is defined as 7 days following the last administration of study diet.

Preexisting Condition

A preexisting condition is one that is present at the start of the study. A preexisting condition should be recorded as an adverse event if the frequency, intensity, or the character of the condition worsens during the study period.

General Physical Examination Findings

At screening, any clinically significant abnormality should be recorded as a preexisting condition. At the end of the study, any new clinically significant findings/abnormalities that meet the definition of an AE must also be recorded and documented as an AE.

Post-study Adverse Event

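### The schedule puts the only scheduled post-discharge adverse event call on Day 24, but the text requires it on Days 12 to 18 and routine follow-up ends on Day 18

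*Combined protocol and SAP*

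**What the plan says.** Four parts of the combined protocol and SAP bear on the timing of this call.

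- **Section 6.3.1 (Visit 4).** The team contacts the participant "by phone once during the week following the completion of the inpatient procedures to assess for any new or unresolved adverse events".
- **Section 8, Adverse Event Reporting Period.** For this study, "the study treatment follow-up is defined as 7 days following the last administration of study diet". AE reporting runs from the first study procedure to the end of that follow-up.
- **Section 6.2, schedule of activities.** Visit 4 is headed Day 24, with no window. The row "AE Follow Up Phone Call" has one mark, under Visit 4. The row "Monitoring adverse events" is marked for Days 1 to 11 and then only for Visit 4.
- **Day 11 sections.** Section 6.1.4 states: "On days 1 and 11, each participant will undergo a sigmoidoscopy to obtain biopsies". Section 6.2.6.6 repeats this for Day 11. Section 6.2.6.11 discharges participants that day, by 5 pm at the latest. Section 6.2.6.8 covers the last food: if the sigmoidoscopy comes straight after the glucose tolerance test, "participants will be given their final meal before discharge".

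**The concern.** The text and the schedule give different dates for the same safety contact, and nothing in the documents reconciles them. The schedule is not background: coordinators book visits from it.

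Participants go home on the day of their second unsedated sigmoidoscopy, at which 16 to 20 biopsies are taken (Section 6.1.4). Section 1.3.1 names bleeding and perforation as the complications. If staff follow the schedule, no AE query is planned for the following week, which is also the whole of the post-discharge reporting period. Events from that week would then depend on the participant reporting them unprompted, or recalling them on Day 24.

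**Working it through.** **Inputs**

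- Discharge and end of inpatient procedures: Day 11 (Sections 6.2.6 and 6.2.6.11).
- Last study diet: Day 11 (Section 6.2.6.8; the randomized diet row of the schedule is also marked through Day 11).
- Length of AE follow-up after the last diet: 7 days (Section 8).
- Visit 4 in the schedule: Day 24 (Section 6.2).

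**Step 1. Is Day 24 what the schedule says?** The header has 4 pre-admission columns + 11 inpatient days + 3 follow-up visits = 18 columns. It has 18 day entries with no blanks. The 16th column is Visit 4 and the 16th entry is 24. The three last entries (24, 48, 107) match the three follow-up visits of Section 6.3, so a shifted column is an unlikely explanation.

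**Step 2. Dates from the text**

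- Week after inpatient procedures: 11 + 1 = Day 12 to 11 + 7 = Day 18.
- End of routine AE follow-up: 11 + 7 = Day 18.

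**Step 3. Discrepancy**

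- Days from discharge to the scheduled call: 24 - 11 = 13.
- Days past both limits: 24 - 18 = 6.

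**Step 4. Do other readings rescue Day 24?**

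- If the last diet is taken as Day 10, follow-up ends on 10 + 7 = Day 17, and Day 24 is 7 days late.
- If the week following means the next calendar week, Day 24 is reached only when Day 11 is the first day of a week (next week = Days 18 to 24). It would still fall after the Section 8 limit of Day 18.

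**Step 5. What each call date covers**

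- A call on Day d within the window can elicit onsets from Day 12 to Day d. It leaves 18 - d days of the reporting period to self-report: 6 days for a call on Day 12, none for a call on Day 18.
- A call on Day 24 reaches all seven onset days, with recall of 24 - 18 = 6 to 24 - 12 = 12 days. A call on Day 18 reaches the same seven days with recall of 0 to 6 days.

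**Step 6. How many procedure complications could be involved?** Section 1.3.1 gives bleeding below 1% and perforation below 0.1%. It does not say per procedure or per participant; I assume per procedure.

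- 20 participants (Study Summary): fewer than 20 × 0.01 = 0.2 bleeds and 20 × 0.001 = 0.02 perforations after the Day 11 procedure.
- 16 completers (Section 4.3): fewer than 0.16 and 0.016.

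**The case against.** The best reply is that this is one stale number in a summary table. Section 6.3.1 and Section 8 agree with each other, and a site that follows the text calls in time. That is fair as to weight, but the schedule is still an operative part of the protocol and it is wrong as written.

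A second reply is that Section 8 says which events must be reported, not when they must be asked about. This stands. A Day 24 call can still elicit everything that began on Days 12 to 18, and a call on Day 12, which the text allows, would cover less of the period. The case against Day 24 is therefore delay and longer recall, not loss of coverage. It is also why the corrected date should aim for Day 18.

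A third reply is that other safeguards exist, and they do. At discharge, "They will be given post-flexible sigmoidoscopy instructions" and an AE log is completed (Section 6.2.6.11). Participants are told to report later events they think related (Section 8). AE questions are asked at every contact, and possibly related serious events after the study period are still reported (Section 8.1). A reader might infer that AE reporting stops outright on Day 18. These provisions show that it does not; only routine follow-up ends then.

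A reader might also infer that Visit 4 is the one follow-up label out of line with its text. The documents do not support that. Section 6.3.2 says: "Participants will provide a stool sample 1 month (+/- 1 week) after discharge". Its 1-month blood draw has no window, and Day 48 is 48 - 11 = 37 days after discharge. Nor do the documents say how Day 24 arose.

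Finally, individual marks in the schedule are imperfect as read. The second sigmoidoscopy mark lines up with Day 10, against Day 11 in Sections 6.1.4 and 6.2.6.6. This may come from the PDF reading, so I rely on the text for the procedure date. The header and the call date are unaffected.

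**Conclusion.** The conflict is real. The schedule places the only scheduled AE phone call after discharge 13 days after Day 11. That is 6 days past both the week set in Section 6.3.1 and the end of routine follow-up set in Section 8. Followed literally, it leaves Days 12 to 18 with no scheduled AE query.

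The consequence is modest. On the protocol's own risk figures, fewer than 0.2 bleeds and 0.02 perforations are expected after the second procedure in 20 participants, and several safeguards remain. A reader might infer that complications would go unrecorded or that the arms would be compared unfairly. The documents give no basis for either: both arms have the same schedule, and no rate of missed events can be derived. No sample size, power or significance figure is affected.

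The conclusion rests on discharge and last study diet both falling on Day 11, as the Day 11 sections state, and on reading the header by column order.

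**What to change.** In the Section 6.2 schedule, change Visit 4 from Day 24 to Day 18 and state a window of Days 12 to 18. Ask staff to aim for Day 18, so that one call covers the full post-discharge reporting period; an earlier call leaves the remaining days to self-report.

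The cost is one day number and one window. The call already exists, so there is no new contact, sample or analysis. The downside is that staff must meet a firm 7-day window, with Day 18 at its edge, so a participant who cannot be reached that day would be contacted late.

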6.3.2 One Month Follow-Up Sample Collection (Visit 5)

Participants will provide a stool sample 1 month (+/- 1 week) after discharge. Participants will return for a blood collection 1 month after discharge. Participants will complete a post study follow up questionnaire at this visit.

6.3.3 Three Month Follow-Up Sample Collection (Visit 6)

In addition, follow-up stool samples (which may be collected every 3 months for up to 5 years after the participant's last study day) may be collected and will be processed in the same manner as the full study. Participants may provide a stool sample every three months (+/- 2 weeks). Participants will complete a post study follow up questionnaire at this visit.

6.4 Sample preparation, processing, and storage at the University of Pennsylvania

6.4.1 Aliquoting and processing of samples for archiving

Stool samples are aliquoted into spoon-capped vials labeled with a barcode that is a unique identifier, the date and a protocol number, usually 6 per sample, for archiving. Any residual stool is aliquoted for specific immediate demands by investigators and/or removed from the collection vessel into up to five 15 ml coring vials, which is also labeled with a similar barcode. Each sample is then scanned, and placed in an -80°C freezer in an appropriate freezer box with its own separate barcode. The freezer box barcode is scanned at the same time. This provides a computerized list of where each sample has been stored which can then be matched with other information that is collected on this sample in the LabVantage lab management system. Blood samples are processed for either serum or plasma, depending on the preservatives added at the time of sampling. Once in the lab, the blood is centrifuged to clear the plasma/serum and the supernatant is measured out in 300-500 ul aliquots into polypropylene cryotubes. Each aliquot is labeled in the same manner as the stool aliquots and immediately placed in a barcoded box in an -80°C freezer to be archived for later use. Finally, when retrieving a stored sample the box and aliquot barcodes are

[figure not shown]

Figure 2. Assessment of microbiota encroachment. Carnoy-fixed biopsies are stained with probes to label bacteria (red), mucus (green), nuclei (blue) or actin (purple). The location of the 5 closest bacteria are measured. 5 fields per sample are analyzed.

scanned and compared to a list of samples needed to ensure the correct material is being removed for use.

6.4.2 Assay for CMC

Levels of CMC in feces and urine will be quantitated by co-investigator [name] at The Penn State University via NMR-based approaches developed by Tajima and colleagues^{34, 35}.

6.4.3 Microbiome characterization

Microbiota localization. For each subject, 4 distal biopsies, collected pre/post CMC and immediately preserved in Carnoy fixative, will be assayed by fluorescence microscopy to determine bacterial localization relative to the epithelium. Specifically, for each specimen, we will examine 5 high-powered fields, selected arbitrarily while blinded to the accompanying clinical data. We will use staining protocols developed by Gunnar Hansson and colleagues^{36, 37} that we have ourselves used extensively in our recent publications^{19, 38}. For each field, we will measure the distance of the 5 closest bacteria per field as illustrated in **Figure 2**. The 25 distances (5 per field x 5 fields) will then be averaged to produce the "average closest bacteria" and compared between groups as reported in our mouse-based studies^{19, 38}. **2) Microbiota composition.** Each fecal sample will be subjected to 16S, metagenomics, and meta-transcriptomic sequence-based analysis as previously described. Sequencing via the Illumina platform (Miseq for 16S, NextSeq500 for metagenomics/transcriptomic). Data will be processed and analyzed via the Qiime platform and R software, in a manner similar to our previous publications^{19, 38-40}. **3) Microbiota pro-inflammatory potential.** For each fecal sample collected, we will measure fecal levels of bioactive flagellin and LPS as reported in our previous publications^{19, 38, 40}. Briefly, for each sample, we will prepare a soluble surface extract to be generated by bead-beating followed by centrifugation. Such samples will be diluted and then applied to cells engineered to express receptors for TLRs 4 or 5 and produce peroxidase under the control of a NF- κ B responsive promoter - our initial publication using this technique describe an extensive set of control studies we have utilized to validate this approach⁴¹. These assays, standardized with E. coli flagellin and LPS will report the levels of bioactive LPS and flagellin, which we have shown are broadly reflective of a fecal specimens ability to drive pro-inflammatory gene expression upon injection into mice⁴¹. Comparison between groups will use t-test, repeated measures ANOVA or analogous non-parametric tests.

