7.1 Sample Size Determination

We will recruit the minimum number of subjects to provide adequate statistical power for the aims of the project. For aim 1, statistical power will depend on the prevalence of detectable CMC in the feces of participants at the end of follow-up. We anticipate that in the CMC treated group, the prevalence will be 100% and in the untreated group the prevalence will be 0%. However, with 8 subjects per group, we will have 89% power to detect a difference if the true prevalence of detectable CMC after 2 weeks of a high dose CMC and CMC free diet are 90% and 10%, respectively. For aim 2, power calculation were based on preliminary data in which the difference in mean distance of the nearest bacteria to the epithelium between patients with and without diabetes was 19.13 μ m. The within group standard deviation (SD) for patients without diabetes was 7.17. The within group SD for those with diabetes was even smaller. With a sample size of 8 subjects per group and assuming a within group SD of 7.17, we will have 90% and 80% power to detect a difference in the distance of the nearest bacteria to the epithelium between the treatment groups (CMC vs. no CMC) that is 35% and 44% smaller than the difference observed between patients with and without diabetes, respectively. In Aim 3, the study will have 80% power to detect a difference between

groups equal to 1.51 units of SD. For paired analyses within treatment groups, there will be 80% power to detect a difference of 1.15 units of SD.

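### Bacterial distance, the only powered Aim 2 outcome, is biopsied on Day 1 and Day 11, but the plan names no between-arm contrast, and the one its power figure implies leaves Day 1 unused

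*Combined protocol and SAP*

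**What the plan says.** **Measurement.** Section 6.1.4: "On days 1 and 11, each participant will undergo a sigmoidoscopy to obtain biopsies". Section 6.4.3 assigns some of these to localization: "For each subject, 4 distal biopsies, collected pre/post CMC and immediately preserved in Carnoy fixative". Both arms therefore supply a value before and after the intervention.

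**Analysis.** Section 6.4.3 says the 25 distances from a specimen "will then be averaged to produce the 'average closest bacteria' and compared between groups as reported in our mouse-based studies". It names no day, change score or baseline adjustment. The section closes with "Comparison between groups will use t-test, repeated measures ANOVA or analogous non-parametric tests". That sentence follows the flagellin and LPS item, so it is unclear whether it also covers localization.

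**Section 7.2.** Distance does not appear. Section 7.2.1 names a Day 11 comparison for microbiome composition and keeps repeated measures ANOVA for fecal samples. Section 7.2.3 lists Day 1, Day 11 and change for the glucose tolerance curves, so the authors do specify time points for other outcomes.

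**Power.** Section 7.1 takes preliminary data in which the difference "between patients with and without diabetes was 19.13" µm. "The within group standard deviation (SD) for patients without diabetes was 7.17". With 8 per group it claims 90% and 80% power for between-arm differences 35% and 44% smaller than that. It gives no day, alpha or sidedness.

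**Status.** Section 3.2 says that this is not an efficacy study and that no efficacy or safety endpoints are pre-specified.

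**The concern.** An outcome measured before and after treatment in two randomized arms allows several between-arm analyses: Day 11 values, change from Day 1, or Day 11 adjusted for Day 1. They estimate the same effect under randomization, but with different precision, and in one small dataset they can fall on different sides of 0.05. If none is named in advance, the choice can be made after the data are seen. A power figure also has meaning only for a named test.

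There is a second cost. If the test implied by section 7.1 is the intended one, the Day 1 biopsies add nothing to the treatment comparison for this outcome, although every participant undergoes them.

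The issue is separate from how many specimens or fields each participant contributes. It remains after the data are reduced to one value per participant per visit.

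**Working it through.** **Inputs.** From section 7.1: reference difference 19.13 µm, SD 7.17 µm, 8 per arm. Assumed: two-sided 0.05, normal data, the same SD on both days and in both arms, and one value per participant per visit. The Day 1 to Day 11 correlation r is not in the documents, so a range is shown.

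**Step 1: the plan's own power.** Differences: 19.13 × 0.65 = 12.43 µm and 19.13 × 0.56 = 10.71 µm. In SD units: 12.43/7.17 = 1.73 and 10.71/7.17 = 1.49. Noncentrality = difference / (7.17 × √(2/8)), which is 3.47 and 2.99, on 14 degrees of freedom.

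| Calculation | 12.43 µm | 10.71 µm |
|---|---|---|
| Stated in 7.1 | 90% | 80% |
| Two-sided t-test | 89.7% | 79.3% |
| One-sided t-test | 95.0% | 88.4% |
| Two-sided normal approximation | 93.4% | 84.8% |

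The stated figures match a two-sided, unpaired t-test on a single occasion with the raw between-subject SD. Day 1 precedes CMC, so the natural occasion is Day 11.

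**Step 2: power of the alternatives at 10.71 µm.** The SD of change is 7.17 × √(2(1 − r)). The adjusted analysis has residual SD 7.17 × √(1 − r²) on 13 degrees of freedom, and its power was simulated so that chance Day 1 imbalance is included.

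| r (assumed) | SD of change (µm) | Day 11 | Change | Day 11 adjusted for Day 1 |
|---|---|---|---|---|
| 0 | 10.14 | 79% | 50% | 76% |
| 0.2 | 9.07 | 79% | 59% | 77% |
| 0.3 | 8.48 | 79% | 65% | about 80% |
| 0.5 | 7.17 | 79% | 79% | 87% |
| 0.7 | 5.55 | 79% | 95% | 96% |

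At r = 0.1 the adjusted analysis also has about 76%. The section 7.1 power carries over to a change analysis only if r is about 0.5 or more.

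**Step 3: do Day 11 and change agree?** These results come from simulations of 40,000 to 60,000 trials per setting.

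- At 10.71 µm they disagree on significance in about 28%, 24% and 21% of trials at r = 0.3, 0.5 and 0.7. At r = 0.5, for example, Day 11 is significant in 79.2%, change in 79.3% and at least one in 91.4%. Both are then significant in 79.2 + 79.3 − 91.4 = 67.1%, and they disagree in 91.4 − 67.1 = 24.3%.
- Significant results in opposite directions occurred in none of 60,000 trials at 10.71 µm for any r tested from 0 to 0.7, and in at most 0.013% with no effect.
- With no effect, claiming on whichever of the two is significant gives 9.0% to 9.6% false positives instead of 5%.

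**Step 4: an illustration.** Suppose chance leaves the arms 8 µm apart on both days. On Day 11, t = 8 / (7.17 × √(2/8)) = 2.23 on 14 degrees of freedom, p = 0.043. The difference in change is zero.

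**The case against.** **The power text already points to Day 11.** It reproduces only as a single-occasion unpaired test, and section 7.2.1, which covers mucosal samples, uses Day 11 for composition. This stands in part: Day 11 between arms is the natural default. But section 7.2.1 concerns composition, section 7.1 names no day, and the closing sentence of 6.4.3, if it applies, offers a menu that includes repeated measures ANOVA. Reference to earlier mouse studies does not put a contrast into this plan.

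**The study is exploratory.** This stands and limits the weight of the point. Section 3.2 disclaims efficacy and safety endpoints, and localization is one of several components of Aim 2. Still, section 7.1 claims power for this comparison, and that claim needs a test attached to it.

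**Naming the Day 11 t-test would also close the gap.** True. Preferring adjustment is a judgment about efficiency, and it loses slightly when r is low.

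**Stronger readings to avoid.** A reader might infer that the contrasts can give opposite answers about direction; Step 3 shows that they differ on significance only. A reader might also count a pre/post test within the CMC arm as a third permitted route, which would raise the false-positive rate to 12% to 13%. The documents do not support that. Sections 6.4.3 and 7.1 both describe a between-group comparison, the pre/post phrase describes when biopsies are taken, and the paired-power sentence in 7.1 follows Aim 3.

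**Conclusion.** The concern holds in a limited form. The only powered Aim 2 outcome is measured twice in both arms, and the plan does not say which between-arm contrast carries it. The power figures are not wrong: they reproduce for an unpaired single-occasion test, most naturally Day 11, and that test leaves the Day 1 values unused.

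Leaving the choice open means about 21% to 28% disagreement on significance between Day 11 and change at 10.71 µm, and about 9% false positives if either may be claimed. Both sizes rest on normal data, equal SDs and two-sided 0.05; the disagreement range also rests on an assumed r of 0.3 to 0.7. The 9% further assumes that the more favorable result would be reported.

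The consequence is for how firmly the Aim 2 localization result can be read. No primary efficacy claim is affected, because the plan makes none.

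**What to change.** Add to section 7.2: *The main localization analysis is a linear model of the participant-level mean Day 11 distance on arm, with the participant-level mean Day 1 distance as covariate, tested at two-sided 0.05. Unadjusted Day 11, change, and within-arm pre/post comparisons are supportive.*

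In section 7.1, state that the 90% and 80% figures are for the unadjusted Day 11 t-test at two-sided 0.05. They should not be presented as a conservative figure for the adjusted analysis, because that does not hold at low r. In section 6.4.3, say whether the closing sentence on tests applies to localization.

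The within-arm comparison should stay supportive because it cannot separate CMC from anything that shifts both arms. With an assumed shared shift of 5 µm, r = 0.5 and no CMC effect, it is significant in 40% of simulated trials, against 5% for each between-arm test.

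Cost: a short text change, with no new samples or visits. The adjusted analysis uses one degree of freedom. At 10.71 µm it gives up as much as about 3 points of power (76% against 79%) if r is near zero, breaks even at about r = 0.3, and gains about 8 points at r = 0.5 and 17 at r = 0.7.
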